**10 GLOSSARY OF TERMS**

Term	Definition
Complete Abstinence	Complete Abstinence is defined as complete avoidance of heterosexual intercourse and is an acceptable form of contraception for all study drugs. This also means that abstinence is the preferred and usual lifestyle of the patient. This does not mean periodic abstinence (e.g., calendar, ovulation, symptothermal, profession of abstinence for entry into a clinical trial, post-ovulation methods) and withdrawal, which are not acceptable methods of contraception. Women must continue to have pregnancy tests. Acceptable alternate methods of highly or less effective contraception's must be discussed in the event that the subject chooses to forego complete abstinence.

## 11 LIST OF ABBREVIATIONS

Term	Definition
ACR	American College of Rheumatology
ACTH	adrenal corticotropic hormone
ADR	adverse drug reaction
AE	adverse event
ALT	alanine aminotransferase (SGPT - serum glutamic pyruvate transaminase)
ARDS	acute respiratory distress syndrome
AST	aspartate aminotransferase (SGOT - serum glutamic oxaloacetic transaminase)
AZA	Azathioprine
β-HCG	beta-human chorionic gonadotrophin
BA/BE	bioavailability/bioequivalence
BCG	Bacillus Calmette–Guérin
BMS	Bristol-Myers Squibb
BP	blood pressure
BUN	blood urea nitrogen
C	Celsius
CA	Contrast Agent
CAD	Computer assisted diagnosis
CDASI	Cutaneous Dermatomyositis Disease Area and Severity Index
CDC ACIP	Center for Disease Control Advisory Committee on Immunization Practices
CFR	Code of Federal Regulations
CI	confidence interval
cm	Centimeter
COPD	Chronic Obstructive Pulmonary Disease
CPK/CK	creatine phosphokinase
CRF	Case Report Form, paper or electronic
CT	computed tomography
CXR	chest X-ray

Term	Definition
DAD	diffuse alveolar damage
D/C	Discontinue
DILI	Drug Induced Liver Injury
DLCO	diffuse capacity for carbon monoxide
DM	Dermatomyositis
DMARD	disease-modifying antirheumatic drug
DNA	Deoxyribonucleic Acid
DOI	Definition of Improvement
ECG	Electrocardiogram
ECL	Electrochemiluminescence
eCRF	electronic Case Report Form
EDC	electronic Data Capture
e.g.	exempli gratia (for example)
EIA	Enzyme Immunoassay
EMG	Electromyography
ER	exposure response
EU	European Union
FDA	Food and Drug Administration
FEV1	forced expiratory volume in 1 second
FI-2	Myositis Function Index
FSH	follicle stimulating hormone
FVC	forced vital capacity
g	Gram
GCP	Good Clinical Practice
GGO	Ground Glass Opacities
GGT	gamma-glutamyl transferase
HAQ-DI	Health Assessment Questionnaire-Disability Index
HBcAb	Hepatitis B core antibody
HBsAg	Hepatitis B surface antigen
HcAb	Hepatitis C antibody

Term	Definition
HCV	Hepatitis C virus
HIPAA	Health Insurance Portability and Accountability Act
HIV	Human Immunodeficiency Virus
HPV	Human papilloma virus
HRCT	high-resolution computed tomography
HRT	hormone replacement therapy
ICH	International Conference on Harmonization
i.e.	id est (that is)
IEC	Independent Ethics Committee
IIM	Idiopathic Inflammatory Myopathy; Idiopathic Inflammatory Myositis
ILD	interstitial lung disease
IMACS	International Myositis Assessment and Clinical Studies group
IMACS DOI	IMACS Definition of Improvement
IMP	investigational medicinal products
IND	Investigational New Drug Exemption
INH	Isoniazid
IRB	Institutional Review Board
ISR/T	investigator sponsored research/trial
ITT	intent-to-treat
IU	International Unit
IV	Intravenous
IVIG	Intravenous Immunoglobulin
IVRS	interactive voice response system
JIA	juvenile idiopathic arthritis
Kg, kg	Kilogram
L	Liter
LDH	lactate dehydrogenase
LT	long term
MDAAT	Myositis Disease Activity Assessment Tool
MDI	Myositis Damage Index

Term	Definition
mg	Milligram
µg	Microgram
MHC	major histocompatibility complex
min	Minute
mL	Milliliter
mmHg	millimeters of mercury
MMR	Measles, mumps and rubella
MMT	Manual Muscle Test
MOA	Mode of Action
MRC	Myositis response criteria
MRI	magnetic resonance imaging
MSD	meso-scale discovery
MTX	Methotrexate
N	number of subjects or observations
N/A	not applicable
NIMP	non-investigational medicinal products
NSAID	nonsteroidal anti-inflammatory drug
NSIP	nonspecific interstitial pneumonia
OP	organizing pneumonia
OR	odds ratio
PBMC	Peripheral Blood Mononuclear Cell
PD	Pharmacodynamics
PFT	Pulmonary Function Testing
PGA	Physician Global Assessment of Disease Activity
PK	Pharmacokinetics
PM	Polymyositis
PPD	Purified Protein Derivative
PRO (ePRO)	Patient-Reported Outcomes (electronic Patient-Reported Outcomes)
PROMIS	Patient-Reported Outcomes Measurement Information System
QLF	quantitative lung fibrosis

Term	Definition
RA	Rheumatoid Arthritis
RBC	red blood cell
RNA	Ribonucleic Acid
ROW	Rest of World
SAE	serious adverse event
SC	Subcutaneous
SCIG	Subcutaneous immunoglobulin
SD	standard deviation
SGA	Patient (Subject) Global Assessment of Disease Activity
SOC	system organ class
ST	short term
Subj	Subject
TB	Tuberculosis
UIP	usual interstitial pneumonia
ULN	Upper-Limit of Normal
UV	Ultraviolet
VAS	visual analog scale
WBC	white blood cell
Wk, wk	Week
WOCBP	women of childbearing potential

## **APPENDIX 1      HIGHLY EFFECTIVE METHODS OF CONTRACEPTION**

At a minimum, subjects must agree to use one highly effective method of contraception as listed below:

### **HIGHLY EFFECTIVE METHODS OF CONTRACEPTION**

Highly effective methods of contraception have a failure rate of < 1% when used consistently and correctly. WOCBP and female partners of male subjects, who are WOCBP, are expected to use one of the highly effective methods of contraception listed below. Male subjects must inform their female partners who are WOCBP of the contraceptive requirements of the protocol and are expected to adhere to using contraception with their partner. Contraception methods are as follows:

1. Progestogen only hormonal contraception associated with inhibition of ovulation.
2. Hormonal methods of contraception including oral contraceptive pills containing combined estrogen + progesterone, vaginal ring, injectables, implants and intrauterine devices (IUDs) such as Mirena®
3. Nonhormonal IUDs, such as ParaGard®
4. Bilateral tubal occlusion
5. Vasectomised partner with documented azoospermia 90 days after procedure
  - Vasectomised partner is a highly effective birth control method provided that partner is the sole sexual partner of the WOCBP trial participant and that the vasectomised partner has received medical assessment of the surgical success.
6. Intrauterine hormone-releasing system (IUS).
7. Complete abstinence
  - Complete abstinence is defined as the complete avoidance of heterosexual intercourse (refer to Glossary of Terms)
  - Complete abstinence is an acceptable form of contraception for all study drugs and must be used throughout the duration of the study treatment (plus 5 half-lives of the investigational drug plus 30 days).
  - It is not necessary to use any other method of contraception when complete abstinence is elected.
  - Subjects who choose complete abstinence must continue to have pregnancy tests as specified in [Section 5.1](#).
  - Acceptable alternate methods of highly effective contraception must be discussed in the event that the subject chooses to forego complete abstinence.
  - The reliability of sexual abstinence needs to be evaluated in relation to the duration of the clinical trial and the preferred and usual lifestyle of the subject.

Local laws and regulations may require use of alternative and/or additional contraception methods.

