### 3) Age and Reproductive Status

- a) Men and Women, age  $\geq 18$  or age of majority
- b) Women of childbearing potential (WOCBP) must have a negative serum or urine pregnancy test (minimum sensitivity 25 IU/L or equivalent units of HCG) within 24 hours prior to the start of study drug.
- c) Women must not be breastfeeding
- d) WOCBP must agree to follow instructions for method(s) of contraception for the duration of treatment with study drug(s) (abatacept) plus 5 half-lives of study drug (70 days) plus 30 days (duration of ovulatory cycle) for a total of 100 days post-treatment completion
- e) Men who are sexually active with WOCBP must agree to follow instructions for method(s) of contraception for the duration of treatment with study drug(s) (abatacept) plus 5 half-lives of the study drug (70 days) plus 90 days (duration of sperm turnover) for a total of 160 days post-treatment completion. In addition, male subjects must be willing to refrain from sperm donation during this time.
- f) Azoospermic males are exempt from contraceptive requirements. WOCBP who are continuously not heterosexually active are also exempt from contraceptive requirements, and still must undergo pregnancy testing as described in this section.

Investigators shall counsel WOCBP, and male subjects who are sexually active with WOCBP, on the importance of pregnancy prevention and the implications of an unexpected pregnancy. Investigators shall advise on the use of highly effective methods of contraception ([Appendix 1](#)), which have a failure rate of  $< 1\%$  when used consistently and correctly. It is expected that investigators will refer to the Product Insert, as well as local regulations and guidelines for prevention of pregnancy appropriate for the standard background treatment being used by individual subjects.

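### Appendix 1 gives one post-treatment duration for complete abstinence, 100 days, which is the women's period and is 60 days shorter than the 160 days the protocol sets for men

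*Protocol*

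**What the plan says.** Protocol Section 3.3.1, under Age and Reproductive Status, sets two post-treatment contraception periods. Criterion 3)d), for WOCBP, is "5 half-lives of study drug (70 days) plus 30 days (duration of ovulatory cycle) for a total of 100 days". Criterion 3)e), for men sexually active with WOCBP, is "5 half-lives of the study drug (70 days) plus 90 days (duration of sperm turnover) for a total of 160 days".

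The counselling paragraph that follows is addressed to both sexes: "Investigators shall counsel WOCBP, and male subjects who are sexually active with WOCBP, on the importance of pregnancy prevention". Its next sentence, "Investigators shall advise on the use of highly effective methods of contraception", is the one that cites Appendix 1.

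Appendix 1 opens without restriction by sex: "At a minimum, subjects must agree to use one highly effective method of contraception as listed below". It introduces its list as methods for WOCBP and for male subjects' partners who are WOCBP. It adds "Male subjects must inform their female partners who are WOCBP of the contraceptive requirements of the protocol" and expects men to keep to contraception with their partner.

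Item 7 of that list, complete abstinence, is the only item that carries a post-treatment duration. It says abstinence "must be used throughout the duration of the study treatment (plus 5 half-lives of the investigational drug plus 30 days").

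**The concern.** The 30-day increment in item 7 is the ovulatory-cycle allowance from criterion 3)d). It has no bearing on a man, for whom the protocol's own rationale is a 90-day sperm turnover. Item 7 is nonetheless worded for any subject who chooses abstinence, and it sits in an appendix that applies to men.

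Item 7 also says that someone who elects abstinence needs no other method. A site or a male subject working from the appendix is therefore given an end date of day 100 and no prompt to look for a later one. What is at stake is partner protection between day 101 and day 160 after the last treatment. It is an instruction to sites and subjects, and the trial's inference does not depend on it.

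**Working it through.** **Inputs**

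- Five half-lives of abatacept: 70 days (criteria 3)d) and 3)e)), so the implied half-life is 70 / 5 = 14 days.
- Increment for WOCBP: 30 days (criterion 3)d)).
- Increment for men: 90 days (criterion 3)e)).
- Increment in item 7: 30 days, with no split by sex (Appendix 1).

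**Reproducing the protocol's own totals**

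- WOCBP: 70 + 30 = 100 days, as stated in 3)d).
- Men: 70 + 90 = 160 days, as stated in 3)e).

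**Applying item 7**

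- Item 7, either sex: 70 + 30 = 100 days.
- Difference for WOCBP: 100 − 100 = 0 days.
- Difference for men: 160 − 100 = 60 days, that is days 101 to 160.
- As a share of the male period: 60 / 160 = 37.5%.
- Share of the sperm-turnover allowance that item 7 provides: 30 / 90 = one third.

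**Is the male figure stated anywhere else a reader of item 7 would look?**

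- The 90 days in Appendix 1 item 5 is the time to documented azoospermia after vasectomy, not a post-treatment period.
- The paragraph on teratogenic concomitant drugs names both sexes and refers to label durations for those drugs. It gives no number of days for abatacept.
- The Glossary entry for complete abstinence contains no duration.

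**Are abstinent men exempt, so that the figure is irrelevant to them?** Criterion 3)f) exempts azoospermic men and WOCBP who are continuously not heterosexually active. It has no matching exemption for abstinent men.

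**The case against.** The strongest reply is that item 7 was written for women. One of its bullets requires subjects who choose abstinence to continue pregnancy tests, which can only mean women, and the Glossary says the same of women explicitly. Read that way, the 30 days is correct and agrees with 3)d). This probably explains how the figure arose. It does not restrict the item: the list is introduced for male subjects' partners as well as for WOCBP, and abstinence is a method a man can choose for himself.

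The second reply is that 3)e) and item 7 address nearly separate groups. Criterion 3)e) begins "Men who are sexually active with WOCBP must agree to follow instructions for method(s) of contraception", so a wholly abstinent man may fall outside its literal wording, and a man who resumes activity with a WOCBP before day 160 falls squarely within it. The Glossary accepts abstinence only as a usual way of life and rejects abstinence declared for trial entry. Item 7 itself asks for the reliability of abstinence to be evaluated and for other methods to be discussed if it is abandoned. All of this stands, and it keeps the practical consequence small. But if 3)e) does not literally reach an abstinent man, item 7 is the only explicit duration he has, and it is the wrong one.

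A third reply is that Section 3.3.1 is the governing text and cites Appendix 1 for which methods qualify, not for how long. That is fair as far as it goes, but item 7 does state a duration, and it does not refer back to the criteria.

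**Conclusion.** The inconsistency is real and minor. Item 7 states 100 days for everyone, whereas the protocol's period for men is 160 days, a shortfall of 60 days. The conclusion rests on the protocol's own 70-day figure for five half-lives and on reading Appendix 1 as covering male subjects, which its introductory text supports.

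The number of men who would rely on abstinence is not given and is probably small. Men on teratogenic background drugs must also follow the durations in those labels. The consent pages are not among the documents available, so what male subjects are actually told cannot be judged. Sample size, power, endpoints and analyses are unaffected.

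**What to change.** In Appendix 1 item 7, replace the parenthesis with a duration for each sex: five half-lives plus 30 days (100 days) for WOCBP, and five half-lives plus 90 days (160 days) for male subjects, with a cross-reference to Section 3.3.1 criteria 3)d) and 3)e).

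This is one wording change at the next protocol revision. It adds no procedures, visits or data.

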### **UNACCEPTABLE METHODS OF CONTRACEPTION**

1. Periodic abstinence (calendar, symptothermal, post-ovulation methods)

2. Withdrawal (coitus interruptus)
3. Spermicide only
4. Lactation amenorrhea method (LAM)

#### **TREATMENT WITH TERATOGENIC CONCOMITANT MEDICATION**

Males and females taking a concomitant teratogenic medication should follow contraception guidelines and duration described in the label for the concomitant medication in addition to those required for abatacept.

## APPENDIX 2      LABORATORY GUIDELINES: PATIENT STUDIES (REVISED AUGUST 13, 1999)

Laboratory test results, which meet these criteria, and the Investigator feels is clinically relevant should be described on the Adverse Event Form. Those which are judged to be SERIOUS events require the completion of a Serious Adverse Event Form (see [Sections 6.1.1](#) and [6.3](#)).

[NOTE: LLN = lower limit of normal; ULN = upper limit of normal.]

**albumin** -  $< 0.9 \times \text{LLN}$  or if pretreatment value is  $< \text{LLN}$ ,  $< 0.75 \times \text{pretreatment}$

**alkaline phosphatase** -  $> 2 \times \text{ULN}$ ; or if pretreatment  $> \text{ULN}$ ,  $3 \times \text{pretreatment value}$

**basophils (%)** -  $> 3\%$  if 0-1% pretreatment,  $> 3 \times \text{pretreatment value}$  if pretreatment  $> 1\%$

### **bilirubin**

a. direct -  $> 1.5 \times \text{ULN}$ , or if pretreatment above ULN,  $> 2 \times \text{pretreatment}$

b. total -  $> 2 \times \text{upper limit of normal}$ , or if pretreatment above ULN,  $> 4 \times \text{pretreatment value}$

**blasts** -  $> 0$

**blood urea nitrogen (BUN)** -  $> 2 \times \text{pretreatment}$

**calcium** -  $< 0.8 \times \text{LLN}$  or  $> 1.2 \times \text{ULN}$ ;  $< 0.75 \times \text{pretreatment}$  if pretreatment below LLN, or  $> 1.25 \times \text{pretreatment}$  if pretreatment above ULN;  $> \text{ULN}$  if  $< \text{LLN}$  pretreatment, or  $< \text{LLN}$  if  $> \text{ULN}$  pretreatment

**chloride** -  $< 0.9 \times \text{LLN}$  or  $> 1.1 \times \text{ULN}$ ; or  $< 0.9 \times \text{pretreatment}$  if pretreatment below LLN, or  $> 1.1 \times \text{pretreatment}$  if pretreatment above ULN;  $> \text{ULN}$  if  $< \text{LLN}$  pretreatment, or  $< \text{LLN}$  if  $> \text{ULN}$  pretreatment

**creatinine** -  $> 1.5 \times \text{pretreatment value}$

**eosinophils (%)** -  $> 3 \times \text{pretreatment}$  and  $> 8\%$  if pretreatment normal; if pretreatment  $> \text{ULN}$ ,  $> 3 \times \text{pretreatment}$

**erythrocytes** -  $< 0.75 \times \text{pretreatment value}$

**glucose** -  $< 0.8 \times \text{LLN}$  or  $> 1.5 \times \text{ULN}$ ; if pretreatment  $< \text{LLN}$  then  $< 0.8 \times \text{pretreatment}$ ; if pretreatment  $> \text{ULN}$  then  $> 2 \times \text{pretreatment}$ ;  $< \text{LLN}$  if  $> \text{ULN}$  pretreatment, or  $> \text{ULN}$  if  $< \text{LLN}$  pretreatment

**hematocrit** -  $< 0.75 \times \text{pretreatment}$

**hemoglobin** -  $> 3 \text{ g/dL}$  decrease from pretreatment value

**lactic dehydrogenase (LDH)** -  $> 1.5 \times \text{ULN}$ ; if pretreatment value is above ULN,  $> 3 \times \text{pretreatment value}$

**leukocyte (WBC) count** -  $< 0.75 \times \text{LLN}$  or  $> 1.25 \times \text{ULN}$ ;  $< 0.8 \times$  pretreatment if pretreatment  $< \text{LLN}$  or  $> 1.2 \times$  pretreatment if pretreatment  $> \text{ULN}$ ;  $> \text{ULN}$  if pretreatment  $< \text{LLN}$  or  $< \text{LLN}$  if  $> \text{ULN}$  pretreatment

**lymphocytes (%)** -  $< 0.5 \times \text{LLN}$  or  $> 2.0 \times \text{ULN}$ , or  $< 0.5 \times$  pretreatment if below LLN pretreatment;  $> 2.0 \times$  pretreatment if above ULN pretreatment.  $> \text{ULN}$  if  $< \text{LLN}$  pretreatment, or  $< \text{LLN}$  if  $> \text{ULN}$  pretreatment

**monocytes (%)** -  $> 2 \times \text{ULN}$ ;  $> 2 \times$  pretreatment if pretreatment above ULN

**neutrophil count (neutrophils+bands)** -  $< 0.67 \times$  pretreatment if pretreatment  $< 1000/\text{mm}^3$ ; otherwise,  $< 1000/\text{mm}^3$ .

**phosphate** -  $< 0.75 \times \text{LLN}$  or  $> 1.25 \times \text{ULN}$ ;  $< 0.67 \times$  pretreatment value if below LLN pretreatment, or  $> 1.33 \times$  pretreatment if above ULN pretreatment;  $> \text{ULN}$  if  $< \text{LLN}$  pretreatment, or  $< \text{LLN}$  if  $> \text{ULN}$  pretreatment

**platelet count** -  $< 0.67 \times \text{LLN}$  or  $> 1.5 \times \text{ULN}$ ; if below normal pretreatment,  $< 0.5 \times$  pretreatment value and  $< 100,000/\text{mm}^3$

**potassium** -  $< 0.9 \times \text{LLN}$  or  $> 1.1 \times \text{ULN}$ ;  $< 0.9 \times$  pretreatment if pretreatment below LLN, or  $> 1.1 \times$  pretreatment if pretreatment above ULN;  $> \text{ULN}$  if  $< \text{LLN}$  pretreatment, or  $< \text{LLN}$  if  $> \text{ULN}$  pretreatment

**protein, total** -  $< 0.9 \times \text{LLN}$  or  $> 1.1 \times \text{ULN}$ ;  $< 0.9 \times$  pretreatment if below LLN pretreatment, or  $> 1.1 \times \text{ULN}$  if above ULN pretreatment;  $> \text{ULN}$  if  $< \text{LLN}$  pretreatment, or  $< \text{LLN}$  if  $> \text{ULN}$  pretreatment

**SGOT and SGPT (ASAT and ALAT)** -  $> 3 \times$  upper limit of normal; if pretreatment above ULN,  $> 4 \times$  pretreatment value

**sodium** -  $< 0.95 \times \text{LLN}$  or  $> 1.05 \times \text{ULN}$ ;  $< 0.95 \times$  pretreatment if below LLN pretreatment,  $> 1.05 \times$  pretreatment if above ULN pretreatment;  $> \text{ULN}$  if  $< \text{LLN}$  pretreatment, or  $< \text{LLN}$  if  $> \text{ULN}$  pretreatment

**uric acid** -  $> 1.5 \times \text{ULN}$ ; if pretreatment above ULN,  $> 2 \times$  pretreatment value

### **urinalysis**

- a) urinary protein -  $> 1$  gram/24 hours and  $2 \times$  pretreatment value
- b) urinary RBC -  $> 5/\text{HPF}$  or,  $> 4 \times$  pretreatment if pretreatment value  $5/\text{HPF}$
- c) urinary WBC -  $> 5/\text{HPF}$  or,  $> 4 \times$  pretreatment if  $5/\text{HPF}$  pretreatment
- d) creatinine clearance (glomerular filtration rate) -  $< 0.67 \times$  pretreatment value
- e) urine dipstick measurements: Protein, blood, sugar, and acetone- 2+, or if 1+ pretreatment,  $2 \times$  pretreatment. Do not evaluate protein if quantitative protein determination done

**stool hemocult** - positive if negative pretreatment

### **APPENDIX 3 BOHAN AND PETER CLASSIFICATION CRITERIA**

1. Symmetrical weakness, usually progressive, of the limb-girdle muscles
2. Muscle biopsy evidence of myositis
  - Necrosis of type I and type II muscle fibers
  - Phagocytosis
  - Degeneration and regeneration of myofibers with variation in myofiber size
  - Endomysial, perimysial, perivascular or interstitial mononuclear cells
3. Elevation of serum levels of muscle-associated enzymes
  - CK, Aldolase, LD, Transaminases (ALT/SGPT and AST/SGOT)
4. Electromyographic triad of myopathy
  - Short, small, low-amplitude polyphasic motor unit potentials
  - Fibrillation potentials, even at rest
  - Bizarre high-frequency repetitive discharges
5. Characteristic rashes of dermatomyositis

Definite Polymyositis = all first 4

Probable Polymyositis = 3 of first 4

Possible Polymyositis = 2 of first 4

Definite Dermatomyositis = rash + 3 other

Probable Dermatomyositis = rash + 2 other

Possible Dermatomyositis = rash + 1 other

Summary of Key Changes of Revised Protocol 03		
Section Number & Title	Description of Change	
2.1 Good Clinical Practice (3rd paragraph)	
Incorporated
 
 
• ‘If required as per local regulation, serious breaches will be reported by Sponsor or designee to applicable authorities’
 
• ‘(occurring in any country)’
 
• and ‘of 1 or more subjects’.
 
	
2.2 Institutional Review Board/Independent Ethics Committee	Removed ‘BMS’ notation and added ‘Sponsor’ & ‘designee’.	
3.1.2 Double-Blind Period (Day 1 - Week 24)	
Additional text: ‘Rescue therapy will be available for subjects who meet the disease worsening criteria during the double-blind period as defined in Section 3.1.4.’
 
&
 
Subjects who discontinue treatment with study medication during the Double-blind Period will complete the Early Termination visit (which is the same visit as Day 169 visit) (See Table 5.1-2). These subjects must also return on the previously scheduled Double-blind Period Day 169 to complete the Post-Study Drug Efficacy Visit (see Table 5.1-4). The purpose of this visit is to assess all aspects of disease activity to ascertain the impact of study participation for regulatory review. Subjects must also complete 2 follow-up visits (Day 85 and 169) during the 24 week post-treatment follow-up period, to perform safety and laboratory assessments (See Table 5.1-5 Post-Treatment Follow-Up Period). This Period begins on the day of the Early Termination visit and applies only to subjects who do not start commercial abatacept therapy.’
	
3.1.3 Open-Label Period (Week 24 - Week 52)	
Supplementary text ‘Use of immune globulin (intravenous [IVIG] or subcutaneous [SCIG] is permitted during this period.’
 
&
 
‘Subjects who discontinue treatment with abatacept during the Open-Label Period will complete the Early Termination visit for the OL (See Table 5.1-3 day 365 is also the OL ET) and 2 follow-up visits during the 24 week post-treatment follow-up period, to perform safety and
	

Summary of Key Changes of Revised Protocol 03		
Section Number & Title	Description of Change	
	
laboratory assessments. (See Table 5.1-5). If the subject receives treatment with an alternate source of abatacept (Post-Study Drug Program [PSDP] or Commercial), completing this post-treatment follow-up period is not required. Treatment with other biologic therapy is not recommended for at least 70 days (~5 half-lives of abatacept follow-up period.)
	
3.1.4 Rescue Therapy	
Removed the following text ‘The choice of rescue therapy is at the discretion of the investigator; however, rescue treatment may not be abatacept or a prohibited medication (See Section 3.4.2.1).’ & Later in the segment, added ‘The use of rescue therapy is at the discretion of the investigator; however, rescue treatment may not be abatacept or a prohibited medication (See Section 3.4.2.1). Allowable medication are restricted to allowable concomitant medication (Section 3.4.1.1 Standard Treatment). Rescue therapy includes increases in dose of current therapy, addition of therapy and change in therapy, all with some restrictions such that allowable rescue therapy meets the criteria for allowable standard treatment. The following changes are allowable as rescue therapy:’ and sections (1), (2) & (3).
	
3.1.5 Post-Treatment Follow-Up Period	
Removed sections:
 
 
• Double-Blind Period (Day 1 to Wk 24)
 
• Open-Label Period (Wk 24 to Wk 52)
 
• Study Completion (After Wk 52).
 
	
3.2 Post Study Access to Therapy	
Amended title to ‘3.2 Post Study Access to Study Drug’, and included ‘with study drug, ie abatacept’.
	
3.3.4 Screening for Malignancy	
Added the text ‘It is recommended that all’ & ‘at the discretion of the investigator’, at several points. & Last paragraph, removed ‘require approval by’ and added ‘may be discussed with’.
	

Summary of Key Changes of Revised Protocol 03		
Section Number & Title	Description of Change	
3.4.1.1 Standard Treatment	Added the text 'Use of immune globulin (intravenous [IVIG] or subcutaneous [SCIG] is permitted during this period. Addition of any other prohibited medication (Section 3.4.2.1; except IVIG3.4.2.1) is not permitted' to the last paragraph.	
3.4.1.3 Immunosuppressant medications	Provided substantial text revision to clarify what immunosuppressants are permitted	
3.4.2.1 Prohibited Medications	Added text 'All prohibited medication must have been discontinued at least 4 weeks prior to randomization with the exception of immune globulin, rituximab and d-penicillamine which have longer exclusion periods (see 3.3.2). Prohibited medication in this contest refers to immunomodulatory medications for the treatment of IIM which are not included as immunosuppressant medications (Section 3.4.1.3). The following list includes examples of specific prohibited medications.'  Also added/removed several therapies.	
3.4.2.2 Restricted Medications	Developed second bullet-point.	
3.5 Discontinuation of Subjects following any Treatment with Study Drug	Second paragraph: Provided substantial text revision to clarify the requirements for subjects that discontinue	
Table 4-1: Study Drugs for IM101611	Added 'Open Label'.	
Table 5.1-2 Study Evaluations - Double-Blind Period (IM101611)	Added Wk 8 assessments for MMT-8 & MDAAT	
Table 5.1-5	Revised Schedule/T&E 'Title'.	
5.4.1.2 Assessments Performed by Medical Staff: Myositis Response Criteria	Added a 'continuous total improvement score' range '0-100'.	
Table 5.5.1-1 Sampling Schedule	Amended Study Days to reflect '85 Days & 169 Days after Last Dose	
6.1.1 Serious Adverse Event Collection and Reporting	Text revised to clarify the reporting of SAEs and Pregnancies immediately.	

Summary of Key Changes of Revised Protocol 03		
Section Number & Title	Description of Change	
[REDACTED]	[REDACTED]	[REDACTED]
8.4.7 Final Study (Week 52) Analysis	Amended [REDACTED] Section 8.4.7 to reflect 85 days and 169 days post last dose in study	[REDACTED]
8.4.2.1 Primary Efficacy Analysis & Table 8.4.2.2-1 Planned Efficacy Analyses	Replaced 'IMACS score' with 'MMT8, baseline MDAAT, baseline PGA'. Clarifying also 'Time to event (IMACS DOI at 2 consecutive time points) up to Day 169 (Week 24)'	[REDACTED]
11. LIST OF ABBREVIATIONS	Additional abbreviations added.	[REDACTED]
[REDACTED]	[REDACTED]	[REDACTED]
Throughout Revised Protocol 03	Amended 'anti-TIF1-c' 'to anti-TIF1-γ'.	[REDACTED]
Throughout Revised Protocol 03	Grammatical and spelling corrections throughout the document. Also addition of other minor clarifications and correction of typographical errors.	[REDACTED]
